## Abstract

*Clostridium difficile* infection (CDI) has become the most common healthcare-associated infection (HAI) in U.S. hospitals, causing half a million infections and 30,000 deaths annually. CDI ranges from asymptomatic colonization, mild to severe diarrhea, pseudomembranous colitis, toxic megacolon, colonic perforation, and death. Risk factors for CDI include older age, comorbidity, hospitalization, exposure to others with CDI, and antibiotic use. Prevention of healthcare-onset (HO)-CDI has become a priority for hospitals. Hospital prevention measures are limited to modifiable risk factors (i.e., prudent antibiotic use and limiting exposure to *C. difficile*). Hospital exposure to *C. difficile* can occur directly (i.e., hands or clothing of healthcare workers) or indirectly (i.e., environmental surfaces or shared equipment) so infection prevention measures focus on healthcare worker hand hygiene and barrier precautions (i.e., use of gowns and gloves) and cleaning and disinfection of the hospital environment. However, these interventions are limited to symptomatic patients who test positive for CDI. Asymptomatic patients serve as a reservoir for cross-contamination, but microbiological screening for asymptomatic carriage of *C. difficile* is not routinely performed in healthcare. Gloving for all patient contacts may interrupt transmission from asymptomatic patients colonized with *C. difficile*.

The overall purpose of the study is to determine the effectiveness of healthcare worker use of gloves for all patient contact for reducing acquisition of *C. difficile* and HO-CDI in inpatient hospital units. The main objective of the study is to compare the effects of universal gloving for all patient contact to the current standard of care (i.e., glove and gown use only for known CDI cases). The aims of the study are:

- 1) Compare the effects of universal gloving for all patient contact to the current standard of care on *C. difficile* acquisition rates in hospitalized patients;
- 2) Compare the effects of universal gloving compared to standard of care gloving on CDI rates, other HAIs, 30-day mortality, and unit length of stay; and
- 3) Describe intervention fidelity, cost, and stakeholder (patients' and healthcare workers') experiences with universal gloving.

The study will be a cluster randomized trial (CRT) in ten inpatient VA hospital units. Units will be randomized either to implement barrier precautions for all patient contacts (universal gloving intervention) or continue standard of care (barrier precautions for patients with known CDI and other antibiotic-resistant organisms). The intervention will consist of all healthcare workers (nurses, providers, respiratory therapists, radiology/laboratory technicians, etc.) utilizing gloves for all patient contacts in the units randomized to receive the intervention. Unit-level data, including *C. difficile* acquisition and infection rates, mortality, length of stay, and barrier precaution compliance, will be collected monthly from all participating sites.

If universal gloving is found to be effective in reducing *C. difficile* acquisition and subsequent infection (and its associated morbidity, mortality, and costs), the results will change the paradigm for CDI prevention in healthcare settings.

## List of Abbreviations

AE	Adverse Event
CAUTI	Catheter-associated Urinary Tract Infection
CDC	Centers for Disease Control and Prevention
CDI	Clostridium difficile infection
CLABSI	Central Line-associated Bloodstream Infection
CP	Contact Precautions
CRT	Cluster Randomized Trial
CTSP	Centralized Transcription Services Program
HAI	Healthcare-associated Infection
HIPAA	Health Information Portability and Accountability Act
HO-CDI	Hospital Onset- Clostridium difficile Infection
ICU	Intensive Care Unit
IPEC	Inpatient Evaluation Center
IRB	Institutional Review Board
LAR	Legally Authorized Representative
LSI	Local Site Investigator
MDRO	Multidrug-Resistant Organism
MRSA	Methicillin-Resistant Staphylococcus aureus
PCR	Polymerase Chain Reaction
PHI	Personal Health Information
PI	Principal Investigator
PII	Personally Identifying Information
RA	Research Assistant
SAE	Serious Adverse Event
VA	Department of Veterans Affairs

## 2.0 Introduction

*Clostridium difficile* is the major infectious cause of healthcare-associated diarrhea, causing as many as 25% of cases. *C. difficile* infection (CDI) affects 500,000 Americans each year, is responsible for 29,000 deaths annually, and has an estimated annual cost of \$ 1.1 billion in the US. Prevention of CDI is essential, and is a critical patient safety issue. Transmission of highly antimicrobial-resistant *C. difficile* occurs primarily in healthcare facilities, where studies have found *C. difficile* acquisition in 1–13% of patients hospitalized for less than a week and in 50% of patients hospitalized for more than 4 weeks. Containment of CDI has been designated a public health priority by several federal agencies, including the VA.

Based on evidence-based guidelines from the Infectious Diseases Society of America, the VA Multidrug Resistant Organism (MDRO) Program Office developed and mandated a multifaceted national bundle for prevention of CDI at VA facilities in 2012 which includes:  1) rapid, appropriate diagnostic testing for *C. difficile*, 2) empiric isolation for patients with diarrhea and suspected CDI, 3) contact isolation for patients with confirmed CDI, 4) environmental decontamination of rooms of patients with CDI, and 5) strategies for improving healthcare worker hand hygiene. However, decreases in CDI rates have been modest, variable and inconsistent. A major reason for this finding is that these interventions are limited to symptomatic patients who test positive for CDI. This is a gap because asymptomatic patients are a major reservoir of *C. difficile*, colonization greatly increases the risk of infection and

importation of CDI from the community to the hospital is increasing. Yet, there is a paucity of evidence on how to reduce transmission from asymptomatic patients.

The two main potential approaches to tackling transmission from the reservoir of colonized patients are to undertake regular microbiological screening or to implement universal contact precautions. The efficacy of these approaches is yet unknown. Microbiological screening at admission to detect asymptomatic carriage of *C. difficile* and place colonized patients in contact precautions is not favored by front-line healthcare workers because it is costly, labor-intensive and requires microbiology resources at each site. Universal gloving where healthcare workers don gloves upon each entry to a patient room regardless of disease state may be promising in reducing the acquisition of CDI because gloves are the most effective means of preventing hand contamination with *C. difficile* spores. Data on universal gowning and gloving is limited to organisms other than *C. difficile* and in ICU settings which cannot be extrapolated to *C. difficile* because *C. difficile* is a spore-forming organism allowing it to remain viable in adverse conditions in the environment for long periods of time and diarrhea leads to heavy, persistent environmental contamination. We hypothesize that current standard of practice that targets glove use for only patients with known CDI does not interrupt *C. difficile* transmission from patients with asymptomatic colonization resulting in *C. difficile* acquisition and subsequent infection. The rationale for the hypothesis is that both patients with active infections and those with asymptomatic colonization serve as reservoirs for patient-to-patient transmission of *C. difficile* either through contaminated healthcare workers hands or contaminated healthcare environment (i.e., patient equipment and/or environmental surfaces). Hand and environmental contamination with *C. difficile* spores are well established and these spores are resistant to both hand hygiene and environmental antisepsis methods.

Hand hygiene is generally accepted to be the most effective means of infection prevention, and current guidance recommends the use of the preferential use of alcohol based hand rubs (ABHR) over soap and water in all clinical situations except 1) when hands are visibly soiled (e.g., blood, body fluids) and 2) after caring for a patient with known or suspected *C. difficile* or norovirus during an outbreak or if endemic rates are high. *C. difficile* spores are not killed by ABHR and may be difficult to remove even with thorough hand washing with soap and water. Strict adherence to gloving is the most effective means of preventing hand contamination with *C. difficile* spores. One study prospectively studied the use of gloves in interrupting *C. difficile* transmission and universal gloving has been proposed as a novel approach to prevent CDI.

Of the two possible approaches to target colonization, screening patients for asymptomatic carriage has increased costs, need for microbiology resources and training, and increased use of contact precautions for those colonized. Universal gloving also results in increased use of contact precautions by gowning and gloving, but the microbiology resources are not necessary. In discussions with VA facilities, there has been much enthusiasm for universal gloving and none for screening and isolation.

### **3.0 Objectives**

The overall goal of our research is to reduce CDI. This proposed study will study the effectiveness of healthcare workers' use of universal gloving for all patient contact in reducing the acquisition of *C. difficile* in hospitalized patients compared with current VA standard care (i.e., healthcare worker glove use when caring for patients in CP isolation) using a pragmatic cluster randomized trial (CRT) in ten inpatient VA hospital units.

We hypothesize that patients with asymptomatic carriage of *C. difficile* can shed the pathogen and therefore are an important reservoir for transmission of *C. difficile*. There are two approaches to target this colonization: microbiological screening of patients to identify those patients who are carriers of *C. difficile* and increased barrier precautions. Microbiological screening for asymptomatic carriage of *C. difficile* is not routinely performed in healthcare because data is limited regarding the use of a detection and isolation intervention to decrease transmission of *C. difficile* and therefore not recommended at present. Here, we propose to implement the use of gloves for all patient contact (i.e., universal gloving) in non-ICU acute care units to prevent transmission of *C. difficile* from both patients with known infections and those patients who are asymptomatic carriers.

We have proposed three objectives:

- To compare the effects of universal gloving for all patient contact to the current standard of care on *C. difficile* acquisition rates in hospitalized patients
- To compare the effects of universal gloving compared to standard of care on CDI rates, other healthcare-associated infections (CLABSI, CAUTI, MRSA), 30-day mortality and unit length of stay.
- To evaluate intervention fidelity (hand hygiene and barrier precaution compliance; glove use for all patients and glove plus gown use for patients in contact precautions (CP) isolation), the cost and stakeholder experiences (interviews and provider-patient contact survey).

This study will be the first to evaluate whether universal gloving will prevent transmission from patients who are asymptotically colonized with *C. difficile* in non-ICU units in an RCT. The study will also investigate the impacts of universal gloving on associated factors, including CDI, other healthcare-associated infections, and their effects on a unit's morbidity, mortality, costs and patients and healthcare workers experience. If the results of the study support universal gloving, it will change the paradigm for prevention of CDI nationwide.

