### **5.2.2 Intervention**

In the units randomized to receive the intervention, all healthcare workers (nurses, providers, respiratory therapist, radiology and laboratory technicians, etc.) will utilize universal gloving (non-sterile gloves) for all patient contacts. If a patient in the intervention unit is known to have CDI or an MDRO, both gowns and gloves will be used as is current standard of care practice for patients in CP isolation. Signage denoting what type of precautions are needed will be placed on the door of each patient's room.

The non-intervention units will follow standard of care which consists of healthcare workers following barrier contact precautions (i.e., gloves plus gowns) only for patients with known CDI and other MDROs (e.g., MRSA).

[figure not shown]

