#### **Intervention Fidelity Data:**

**Hand Hygiene Compliance:** In both the intervention and control groups, hand hygiene compliance will be measured on a random sample of healthcare workers caring for patients. Research staff will perform monthly observations that will be recorded on a standard observation tool; participating site research staff will be trained by study coordinating site research staff. WHO manual for observers recommends observing a minimum of 200 hand

hygiene opportunities during each measurement period in each unit. We estimate the number of hand hygiene opportunities as 10 opportunities per patient per hour. The average unit will have 20 patients, therefore each month research personnel will observe hand hygiene opportunities for one hour to generate the minimum observation of 200 hand hygiene opportunities per unit per month. The data will be uploaded to a shared database on the VA server, unless otherwise specified in a valid DUA.

**Contact Precaution Compliance:** In both the intervention and control groups, barrier precaution compliance (i.e., healthcare worker glove plus gown use during care of patients in CP isolation) will be measured on a random sample healthcare worker contacts during care of patients in CP isolation. Research staff will perform monthly observations that will be recorded on a standard observation tool; participating site research staff will be trained by study coordinating site research staff. We estimate the average number of patient contacts by healthcare workers using barrier precautions to be 60 contacts per day. The average unit will have 2-6 patients (10-30%) in CP isolation; each month research personnel will observe for one hour to generate 10% sample of 12 healthcare worker contacts using minimum estimate of patients in isolation. The data will be uploaded to a shared database on the VA server, unless otherwise specified in a valid DUA.

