**Universal Gloving Compliance:** In the intervention group, universal gloving compliance will be measured on a random sample of healthcare workers caring for patients. Research staff will perform monthly observations that will be recorded on a standard observation tool; participating site research staff will be trained by study coordinating site research staff. We will use hand hygiene opportunity estimates as surrogate for patient contact opportunities requiring gloving. The average unit will have 20 patients, therefore each month research personnel will observe gloving opportunities for one hour to generate the minimum observation of 200 patient contact opportunities per unit per month in the intervention unit only. The data will be uploaded to a shared database on the VA server, unless otherwise specified in a valid DUA.

**Isolation Days of Care:** Contact precautions can be used for reasons other than CDI such as antibiotic resistant organisms (e.g., MRSA). If a large proportion of barrier precautions are being used in the control group for these types of patients, it could confound the study endpoints. To account for this, we will collect and estimate isolation days of care. In both the intervention and control groups, research staff will collect monthly aggregate data on isolation patients from site personnel (i.e., infection control) at participating sites which are collected as standard of care reporting. We will estimate the isolation days of care by multiplying the number of patients on CP isolation by the average length of stay for the participating unit. The data will be uploaded to a shared database on the VA server, unless otherwise specified in a valid DUA.

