**30-Day Mortality:** Using patient level data, we will conduct a 30-day survival analysis to determine the hazard of mortality for control and intervention units using a cox proportional hazards model with Kaplan Meier curves. Within each unit, a risk analysis will be conducted to

determine the predictors of 30-day mortality. Additionally, we will examine survival percentages at specific periods of the intervention period (i.e. 3, 6, 9 and 12 months; or every 3 months of the intervention period) using life tables and log-rank tests to determine at which points mortality was highest for each unit.

*Other clinical outcomes:* Rates of toxic megacolon and colectomy will be compared between intervention and control units using chi-squared test or Fisher's exact test, with post-hoc pairwise comparisons. All incidence and risk analysis will be conducted using Poisson regression models with covariate adjustment. For specific time periods (during 3, 6, 9 and 12 months), we will use incidence split model to determine the point of highest infection within each unit, with appropriate covariate adjustment. We will use the Royston's trend test to conduct a time-trend analysis on the monthly outcomes.

*Intervention Fidelity:* We will calculate the compliance rates for both the intervention and control units and compare them using a chi-squared test. We will conduct a univariate logistical regression model to determine the odds of compliance with respect to additional unit characteristics such as number of beds and location. Monthly compliance will be modeled using a time series graphing technique with trend analysis estimates.

*Isolation Days of Care:* Monthly aggregate data of isolation patients will be collected from infection control at participating sites which are collected as standard of care and we will estimate the days of care by multiplying this number by the average length of stay for the participating unit. We will make comparisons between the intervention and control groups using the analysis of variance (ANOVA).

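### Gloving compliance is planned only as an all-patient rate, so no planned statistic shows glove use at the non-isolated contacts where the intervention adds it

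*Combined protocol and SAP*

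**What the plan says.** - **Objectives (Section 3.0).** The barrier-precaution part of fidelity is described as "glove use for all patients and glove plus gown use for patients in contact precautions (CP) isolation". Section 5.2.1 repeats this description.
- **Sampling (Section 5.6, Universal Gloving Compliance).** In intervention units, "universal gloving compliance will be measured on a random sample of healthcare workers caring for patients". The text neither excludes nor flags contacts with isolated patients.
- **Sizing (same paragraph).** "The average unit will have 20 patients, therefore each month research personnel will observe gloving opportunities for one hour". The stated aim is to "generate the minimum observation of 200 patient contact opportunities per unit per month in the intervention unit only". The rate behind this comes from the hand hygiene paragraph: "We estimate the number of hand hygiene opportunities as 10 opportunities per patient per hour".
- **Isolated patients (Section 5.6, Contact Precaution Compliance).** "The average unit will have 2-6 patients (10-30%) in CP isolation". Their care is scored separately in both arms, as gloves and gown together.
- **Standard care (Section 5.2.2).** For intervention-unit patients with known CDI or an MDRO, "both gowns and gloves will be used as is current standard of care practice for patients in CP isolation". Control units follow the same practice for such patients.
- **Analysis (Section 5.7.2, Intervention Fidelity).** Compliance rates are compared between arms by a chi-squared test, and "Monthly compliance will be modeled using a time series graphing technique with trend analysis estimates". No split by isolation status is planned.

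**The concern.** The trial adds gloving only at contacts with patients who are not in isolation. These are also the contacts that test the hypothesis of spread from unrecognised carriers. The gloving rate as planned mixes them with contacts where gloves were already required before the trial.

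The mixture matters most if the result is null. The reader then has to decide whether gloving failed to work or was not done, and the gloving rate is the main evidence. If pre-existing glove use at isolated contacts is higher than the new glove use elsewhere, the pooled rate makes uptake look better than it was. A change over months, or a difference between units, could then reflect how many patients were in isolation, with no change in behaviour.

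The plan's other measures cannot recover the missing figure:
- Contact-precaution compliance is a glove-plus-gown composite on about 12 contacts a month, so it gives no glove-only rate.
- Isolation days are a monthly estimate (isolated patients times mean stay) and are not linked to observed contacts.
- Gloving is not observed in control units, so there is no background all-patient rate to subtract.

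**Working it through.** **1. Reproduce the plan's figure.** Opportunities = patients × opportunities per patient-hour × hours = 20 × 10 × 1 = 200. This matches Section 5.6. One hour yields 200 only if all 20 patients count, so isolated patients are in the denominator.

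**2. Isolated patients.** 10% and 30% of 20 are 2 and 6, as stated. Non-isolated opportunities per hour are 18 × 10 = 180 down to 14 × 10 = 140.

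**3. Isolated share of observed contacts, s.** The 10-30% is a share of patients. The share of contacts depends on the contact rate of isolated patients, and Section 5.6 supports three readings:
- *Uniform rate of 10 per patient-hour*, as in the gloving paragraph: 20/200 = 10% to 60/200 = 30%.
- *12 contacts in one hour from 2 isolated patients*, as in the contact-precaution paragraph, or 6 per patient-hour: 12/(12 + 180) = 6% to 36/(36 + 140) = 20%.
- *60 contacts per day*, read as per isolated patient because 10% × 2 × 60 gives the plan's 12. Spread over 24 hours this is 2.5 per patient-hour: 5/(5 + 180) = 2.7% to 15/(15 + 140) = 9.7%.

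**4. Effect of pooling.** Let g be glove compliance at isolated contacts and p at non-isolated contacts. The reported rate is s·g + (1 − s)·p, so the difference from p is s·(g − p). The documents give neither g nor p, so the values below are assumptions.

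| Reading of s | s | g = 90%, p = 40% | g = 90%, p = 60% |
|---|---|---|---|
| Uniform rate | 10-30% | +5 to +15 points | +3 to +9 |
| 6 per patient-hour | 6-20% | +3 to +10 | +2 to +6 |
| 2.5 per patient-hour | 2.7-9.7% | +1 to +5 | +1 to +3 |

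If g = p, the difference is zero at every s. If g = 60% and p = 70%, the uniform reading gives −1 to −3 points, so uptake is understated.

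**5. Dependence on census.** With g = 90% and p = 40%, moving from 2 to 6 isolated patients shifts the reported rate by 0.20 × 50 = 10 points under the uniform reading. Under the lowest reading the shift is (0.097 − 0.027) × 50 = 3.5 points. Behaviour is unchanged in both.

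**6. Cost of looking at non-isolated contacts alone.** The 95% half-width at 50% compliance is 1.96 × √(0.25/n), ignoring clustering by worker. It is 6.9 points at n = 200, 7.3 at 180 and 8.3 at 140. Keeping 200 non-isolated opportunities takes 60 × 200/180 = 67 minutes to 60 × 200/140 = 86 minutes.

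**The case against.** The strongest reply is that the all-patient rate is the right measure of the policy as written. The policy is gloves at every patient contact, and Section 3.0 aims at transmission from known infections as well as from silent carriers. This stands: the overall rate is legitimate and should stay. It does not, however, answer the separate question of whether the added behaviour occurred.

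A reader might infer that reported uptake is inflated. The documents do not support that. Inflation and census dependence both require isolated contacts to be gloved more often than others, and no compliance level is given for either group. Higher compliance with an established precaution than with a new one is plausible, but equal rates give no bias and the opposite order reverses it.

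A reader might also take the 10-30% as the share of observed contacts. It is a share of patients. The plan's own contact rates allow anything from about 3% to 30% of contacts, and hand hygiene opportunities and contacts may not be the same unit.

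The drift should not be pressed far either. Nothing says that a unit moves between 2 and 6 isolated patients from month to month. A shift of a few points would also be hard to see in one unit-month with a half-width near 7 points. A persistent error in the level, though, would not average out with more observation.

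Finally, the observation tool is not in the documents and may already record isolation status. If so, only the reporting plan needs to change.

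**Conclusion.** The point holds as a gap in the fidelity analysis. The gloving rate pools contacts where gloves were already standard with contacts where they are new, and no planned statistic separates them. That much follows from the text alone.

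The size and direction of any distortion are conditional. On an assumed 90% against 40%, the pooled rate overstates uptake by about 1 to 15 points, depending on the isolated share of contacts. The distortion vanishes at equal compliance and changes sign if isolated contacts are gloved less. Without the split, a reader of the results cannot tell which case applies.

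This is a cheap improvement to a fidelity measure. It does not touch the primary outcome, the sample size or the effect estimate.

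**What to change.** - **Section 5.6, Universal Gloving Compliance:** have the observer mark each observed contact as with an isolated or a non-isolated patient, using the door sign that Section 5.2.2 already requires.
- **Section 5.7.2, Intervention Fidelity:** report glove compliance separately for non-isolated and isolated contacts, beside the overall all-patient rate. Use the non-isolated rate and its monthly trend to judge uptake of the new behaviour, and the overall rate for adherence to the policy as written.
- **Keep isolated contacts in the gloving data.** Moving them solely into the glove-plus-gown measure would lose glove-only information, because a gloved but ungowned contact may simply count there as non-compliant.

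The cost is one tick-box on the form and a few lines of text. In addition, either accept 140 to 180 non-isolated opportunities per hour (half-width 7.3 to 8.3 points instead of 6.9) or extend observation to about 67 to 86 minutes per intervention unit per month to keep 200.
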